Specific reproductive toxicology studies on vafidemstat have not been completed. However, no vafidemstat related changes in organ weights and macroscopic/microscopic observation in both ovary and testicles as compared to vehicle control group were observed in the toxicological studies (28-day and long-term studies in rat and dog). Additionally, preliminary embryo-fetal development study to select the doses for the main study has been completed. Results from this study show that low (0.2 mg/kg (HED=3.8 mg)) and mid (0.6 mg/kg (HED=11.5 mg)) doses were well tolerated, without significant changes in the fetal viability or malformation incidence compared to the control group. The high dose (1.8 mg (HED=34.6

mg)) showed high incidence of spontaneous abortion. The tested mid-dose allows for a 10-fold safety margin, considering the highest clinical dose (1.2 mg/day). Available data, along with the double barrier protection in the inclusion criteria of vafidemstat clinical trials, is considered to adequately support the inclusion of women of child-bearing potential.

In vivo Pharmacology

As for its pharmacology properties, vafidemstat has been shown to modulate aggressiveness and other social behavior alterations in different animal models of neuropsychiatric pathologies.

For instance, the SAMP8 male mice are an interesting model to study the aggression associated with AD as well as other dementias. In the resident-intruder test (a standardized experiment to evaluate social interaction, including offensive aggression and defensive behavior) the SAMP8 males show a very aggressive behavior against the intruder mice compared with their control strain SAMR1. Treatment for 6 weeks with vafidemstat diminishes this aggressive behavior at similar levels to those observed in the SAMR1.

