4.1.1. Inclusion Criteria

The participant must meet all inclusion criteria:

1. Men and women 18-65 years of age.
2. DSM-5 diagnostic criteria for BPD at least 3 months before the Screening visit. The Mini-International Neuropsychiatric Interview (MINI) will be administered at screening in order to confirm BPD diagnosis, as well as to confirm participant does not meet other relevant exclusion criteria.
3. Agitation-Aggression Psychiatric Inventory-Clinician Report (AAPI-CR) Agitation & Aggression (A/A) subscale score of ≥ 16 (severity x frequency) summed across the four (4) items comprising the A/A subscale, and the sum of the A/A subscale severity scores ≥ 6 .
4. Stable living environment for > 6 months before the Screening visit.
5. Body mass index (BMI) of at least 18.5 kg/m², but no more than 35 kg/m².
6. Willing and able to adhere to the prohibitions, restrictions and requirements specified in this protocol.
7. Otherwise, healthy and medically stable based on medical history.
8. Clinical and neurological examinations and laboratory tests, as well as 12-lead ECG performed during screening that confirms participant is healthy and medically stable.
9. Able to read and write fluently and must have adequate hearing and visual acuity to complete the required testing outlined in this protocol.
10. Stable in their permitted regimen of background therapy (see section 6.1.2) for concomitant medications at the Screening visit. Participants should maintain treatment throughout the study and not initiate any prohibited medications during the trial, as well as agree to inform their study physician of any medication changes throughout the trial.
11. Enrolled participants will need to maintain their pre-screening psychotherapy schedule throughout the trial duration. That is, participants receiving psychotherapy will need to have it started at least 3 months before the Screening visit and remain in psychotherapy throughout the trial. Participants not receiving psychotherapy should not initiate psychotherapy during the trial.
12. Fertile male and female participants must use highly efficient contraception, from the Screening visit until 30 days after last dose of the IMP, defined as:

A method with less than 1% failure rate (e.g., permanent sterilization, hormone implants, hormone injections, some intrauterine devices, or vasectomized partner)

OR

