7.3.7. Urinalyses

- **Pregnancy test** in urine will be conducted only in females of reproductive age at Visit 1 (Screening Visit), Visit 2 (Baseline) and Visit 8 or EoS Visit. Pregnancy tests can be performed at any point during the study if pregnancy is suspected or as required by local regulations. All positive urine pregnancy test results must be confirmed by a serum test. Pregnancy tests are to be performed by a central laboratory.
- **Drug screening** in urine for illicit drugs will be conducted in all participants at Visit 1 (Screening Visit), and all the study visits from Baseline (Visit 2) to Visit 8 or EoS Visit, including Visit 9 (Safety follow-up). A positive drug screen test is not automatically a withdrawal criterion. However, a positive drug screen test should prompt the investigator to investigate the cause of such a positive test and further evaluate the patient in light of this finding. Before the patient is withdrawn, the sponsor should be consulted. Drug screening urinalyses will be conducted by a central laboratory.

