7.7.11. Classification of participants according to completion of study visits

According to the number of visits, participants can be classified as follows:

- a. *Completers*: Participants completing Visit 9.

- b. *Non-completers*: Participants that received at least one dose of study treatment, but prematurely discontinued the study before completion of Visit 9 for any reason other than withdrawal of the informed consent. These participants will be asked to complete an End of Study (EoS) Visit as soon as possible after withdrawal. Non-completers will not enter the 2-week participant-blind placebo run-out period.
 - i. If there has been, at least, one week between the last intake of study drug and this EoS visit, no further Safety follow-up visit will be required.
 - ii. If there has been less than one week between the last intake of study drug and EoS visit, participant will be asked to attend to a Safety-follow up visit, two weeks after the last intake of study drug, to perform safety assessments only.
- c. *Non-completers who discontinue the study because they withdraw their consent*: Participants that received at least one dose of study treatment, but prematurely discontinued from the study before completion of Visit 9 due to withdrawal of informed consent. These participants, if possible, will be asked to attend to an EoS Visit.
 - i. The visit must be scheduled as soon as possible after withdrawal.
 - ii. If the participant withdraws consent during a visit but agrees to complete the visit, then, the investigator will complete an EoS Visit. All the data collected up to and including this visit will be used in the analysis.
 - iii. If the participant withdraws consent and refuses to complete the EoS Visit, no new information will be collected. However, it is recommended, outside the scope of this study, to perform a safety assessment within 2 weeks after treatment discontinuation.

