8.6. Pregnancy

Female participants will be instructed to notify the PI immediately if they become pregnant during the study. Male participants will be instructed to notify the PI immediately if their partner becomes pregnant. Pregnant participants will be withdrawn from further study treatment. The participants will also be instructed to report pregnancies discovered after the last visit, if they believe that conception occurred during their participation in the study.

A pregnancy as such is not an AE, unless there is a possibility that vafidemstat has interfered with the efficiency of any contraceptive measures. However, the Investigator should report pregnancies according to the procedures and timelines described for reporting of SAEs (Section 8.3). The pregnancy report form should be used instead of the SAE form.

The pregnant participant or partner will be followed until the end of the pregnancy. Any complication during the pregnancy should preferably be reported as an AE. The outcome of the pregnancy must be reported on the pregnancy report form. Any spontaneous abortion, stillbirth, birth defect/congenital anomaly, death, or other serious infant condition must be reported and followed up as an SAE.

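### Section 8.6 asks for pregnancies found after the last visit only if conceived during participation, so conceptions late in the protocol's own 30-day contraception window are not solicited

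*Protocol*

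**What the plan says.** **Contraception.** Protocol Section 4.1.1, criterion 12 (repeated in the Synopsis) says: "Fertile male and female participants must use highly efficient contraception, from the Screening visit until 30 days after last dose of the IMP". Section 1.6 links the contraception requirement to the lack of data on the reproductive system.

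**Reporting.** Section 8.6 contains several instructions with different reach:
- For women: "Female participants will be instructed to notify the PI immediately if they become pregnant during the study".
- For men: tell the investigator if a partner becomes pregnant. No end date is given.
- For participants after the last visit: "report pregnancies discovered after the last visit, if they believe that conception occurred during their participation in the study".
- For the investigator: report pregnancies on the SAE timelines, and follow the participant or partner to the end of the pregnancy. No end date is given.

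**Last contact.** Completers finish at Visit 9, Day 99±2 (Section 7.7.9). Under Section 7.7.11, a non-completer whose EoS visit falls at least one week after the last intake has no later contact: "no further Safety follow-up visit will be required". If the EoS visit is earlier than that, a safety visit is held two weeks after the last intake.

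**Testing.** Section 7.3.7 schedules urine pregnancy tests at "Visit 1 (Screening Visit), Visit 2 (Baseline) and Visit 8 or EoS Visit". Unscheduled tests are allowed during the study.

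**What counts as IMP.** The Synopsis equates IMP with vafidemstat. Section 5.1.2 says IMP is vafidemstat and placebo. Section 9.2 writes of IMP or placebo as two things.

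**The concern.** The protocol sets a precaution period that outlasts the last visit, but its instruction to participants covers only conceptions during participation. A participant who follows Section 8.6 to the letter has no reason to report a conception that falls after the last visit and still inside the period in which contraception was required.

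What is at stake is a small amount of safety information of a kind the programme lacks. Vafidemstat is an irreversible LSD1 inhibitor (Section 1.2). Section 1.3 states that specific reproductive toxicology studies are not complete, and it supports enrolling women of child-bearing potential partly on the contraception requirement. A failure of that safeguard within its own window should be visible to the sponsor.

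**Working it through.** No sample size, power or alpha is involved, and the plan gives no figure to reproduce. The check is a timeline, followed by a search for any other instruction that would close the gap.

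**Inputs.** Contraception window: 30 days after the last dose (4.1.1). Visit 8: Day 85±2; Visit 9: Day 99±2 (7.7.8, 7.7.9). These agree with Day = 7 × week + 1: 7 × 12 + 1 = 85 and 7 × 14 + 1 = 99. From Visit 8 to Visit 9 everyone takes placebo (5.1.1), and the capsule taken at the Visit 8 clinic comes from the new box. The last active capsule is therefore on about Day 84, or Day 85 at the latest on nominal days.

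**Formula.** Unsolicited days = (day of last dose + 30) − day of last visit.

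| Case | Calculation | Days |
|---|---|---|
| Completer, last active capsule Day 84 | 84 + 30 − 99 | 15 |
| Completer, last active capsule Day 85 | 85 + 30 − 99 | 16 |
| Same, visit windows, shortest (Visit 8 Day 83, Visit 9 Day 101) | 82 + 30 − 101 | 11 |
| Same, visit windows, longest (Visit 8 Day 87, Visit 9 Day 97) | 86 + 30 − 97 | 19 |
| Completer, run-out placebo counted as IMP, last capsule Day 98 or 99 | 98 + 30 − 99; 99 + 30 − 99 | 29; 30 |
| Non-completer, safety visit 14 days after last intake | 30 − 14 | 16 |
| Non-completer, EoS visit at least 7 days after last intake | 30 − 7 | at most 23 |

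The two visit-window rows put the last active capsule on the day before Visit 8. If Visit 8 falls on a Monday, the two preceding days are weekend placebo; on nominal days that gives 82 + 30 − 99 = 13, inside the same range.

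A participant who withdraws consent on the last dosing day and declines the EoS visit would have all 30 days uncovered. Section 7.7.11 stops all new data collection for that participant, so this case is separate from the wording of 8.6.

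**Does anything else close the gap?** AE recording ends at the follow-up visit (7.3.1, 8.2). Section 8.2.3 follows only events already ongoing. Unscheduled pregnancy tests are limited to the study period (7.3.7). SAP Section 5.2.7 only lists test results. None of these asks for a conception after the last visit.

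**Expected number.** The documents give no pregnancy rate. Assume that all 94 participants planned for the active arm are fertile and that contraceptive failure is 1% to 10% per year. Over 15 days: 94 × 15/365 × 0.01 = 0.04, and 94 × 15/365 × 0.10 = 0.4 pregnancies. Over 30 days these double, to about 0.08 and 0.8.

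**The case against.** The best defence is that the limit in 8.6 applies only to what participants are told to volunteer after their last visit. The investigator's duties to report and to follow to outcome carry no end date, so a pregnancy that reaches the site on Day 110 would still be reported and followed. This stands. A reader might infer that pregnancies in the gap go unreported or are discarded; the text does not support that. The gap is in solicitation.

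Other points:
- **Partners.** The sentence on male participants' partners has no time limit. This stands in part: the later sentence on pregnancies found after the last visit covers all participants, so the position for men is ambiguous and the gap is clearest for women.
- **Participation is undefined.** It could be read to run as long as the contraception duty. No passage says so, and a participant would naturally take it to end with the visits.
- **The 30-day figure.** A reader might infer up to 30 days of drug-exposed conceptions among completers. That figure needs the run-out placebo to count as IMP. Days 114 to 129 are then 30 to 45 days after the last active capsule.
- **Testing at Visit 9.** A reader might tie the gap to the absence of a pregnancy test there. A test at Visit 9 cannot detect a conception after Visit 9, and conceptions up to that visit are already asked for by 8.6.
- **Toxicology.** Section 1.3 says the high dose "showed high incidence of spontaneous abortion". That dose had a human equivalent of 34.6 mg, about 29 times the 1.2 mg clinical dose (34.6/1.2 = 28.8). The low and mid doses were well tolerated, with a stated 10-fold margin at the mid dose. The argument therefore rests on the incomplete data package, and that finding does not show a hazard at 1.2 mg.

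**Conclusion.** The concern holds as a mismatch between two sections of the protocol. Criterion 12 and Section 8.6 end at different points, and conceptions between the last visit and the end of the contraception window are not solicited, most clearly for women. On nominal days the gap is 15 to 16 days for completers from the last active capsule, or 29 to 30 days if run-out placebo is IMP. For non-completers it is 16 days, or at most 23, depending on the route out of the study. It is present on every reading of IMP; only its length changes.

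This assumes that participation ends at the last visit, which the protocol does not define. On the assumed failure rates, fewer than one pregnancy would be expected in the active arm, and no efficacy or main safety conclusion depends on it. The case for acting is that such reports are rare, the reproductive data are incomplete, and the correction is cheap. Nothing here bears on whether 30 days is the right period.

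**What to change.** Reconcile Sections 4.1.1 (criterion 12, and its copy in the Synopsis) and 8.6 so that the contraception period and the pregnancy-reporting period end at the same point, for participants and for partners. The sponsor should decide what that point is.

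State whether the last dose of the IMP means the last active capsule or the last run-out placebo capsule, and make the Synopsis, Section 5.1.2 and Section 9.2 agree. Match the consent wording.

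The cost is one sentence in 8.6, one definition and the corresponding consent text. The downside is at most a few extra pregnancy reports to follow. No added visit or test is needed.

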9. STATISTICAL METHODS

9.1. Statistical and Analytical Plans

The statistical analysis will be further detailed in a separate statistical analysis plan (SAP). The SAP will be finalized before the interim analysis and any unblinding.

All statistical analyses will be performed using the latest available version of SAS® (SAS Institute Inc., Cary, North Carolina, United States of America [USA]).

9.2. Data sets to be analyzed

With regards to analysis of data, the following analysis sets are defined:

- **Safety Analysis Set (SAF):** All participants who received at least one dose of the study IMP or Placebo.
- **Full Analysis Set (FAS):** All patients enrolled (randomized) in the study. Patients will be analyzed as randomized.
- **Per-Protocol Set (PPS):** All participants in the FAS without any major protocol deviations* as described in Section 10.9 and who also satisfy both of the following constraints:
 1. Have at least completed one CGI-S A/A assessment at specific weeks
 2. Have at least completed one BPDCL assessment at specific weeks

**Important violations of eligibility criteria and other deviations from the protocol will be assessed in cooperation with the Sponsor. Important deviations from the protocol may lead to exclusion of a participant from the PPS. Individuals in the PPS will be analyzed as treated.*

9.3. Statistical Analysis

9.3.1. Use of different analysis sets

Both, SAF and PPS will be used for safety analysis, being SAF considered the primary safety analysis set population. Primary efficacy analysis will be performed using the FAS population. Efficacy will also be tested in the PPS population and used for supplementary and sensitivity analysis.

9.3.2. Handling of missing values

Missing value imputation will be performed as outlined in the SAP, and several additional options for imputing missing values will also be explored as part of the sensitivity analysis (see Section 9.3.11), including multiple imputation.

9.3.3. Summary Statistics

Descriptive statistics (n, mean, standard deviation (SD), median, minimum and maximum) will be provided for continuous variables. Frequency counts (n and percentage) will be provided for qualitative variables. Clinical rating scales may be summarized both as continuous and as qualitative variables, depending on the context. A confidence level of 95% will be used for all confidence intervals unless stated otherwise.

All summary statistics will be provided by randomized or actual treatment arm and by visit and time point (where applicable).

In the listings, participants will be identified using their participant number.

Details will be provided in the SAP.

9.3.4. Primary Efficacy Analysis

The primary efficacy analysis will be performed for the CGI-S A/A and the BPDCL scores (sum of responses for all items).

The estimand for the primary efficacy analysis is defined with the target population determined by the inclusion/exclusion criteria, the endpoints targeted are the primary efficacy endpoints for the study and mean changes from baseline to specific weeks as the population level summary. Intercurrent events that are expected to occur include early treatment discontinuation due to patient choice or due to adverse events both unrelated to the medication or study indication (e.g., Covid-19) and related to the study medication or indication, as well as the initiation and/or discontinuation of psychotherapy during the trial.

The mixed model repeated measures (MMRM) will include as fixed factors: site, visit, treatment arm, psychotherapy at baseline, baseline value of the response variable, the interaction between treatment and visit as well as visit interaction with the baseline value (last measurement prior to treatment initiation) for the endpoint and psychotherapy at baseline. The contrast that will be tested for significance is the difference between active treatment and placebo from baseline to specific week. The study is controlled at a 5% level. The Hochberg correction will be applied. If one endpoint is below the 2.5% level or if both endpoints are below the 5% level of significance the study is declared a success.

Possible alternative analysis methods will be investigated as part of the sensitivity analysis, see Section 9.3.11.

Boxplots will be presented for the changes from baseline to specific week in both endpoints by treatment arm.

Descriptive statistics will also be presented.

Full details on the primary analysis will be documented in the SAP and supersede what is outlined in the protocol.

9.3.5. Secondary Efficacy Analysis

The same MMRM as for the primary analysis will be calculated without a formal confirmatory significance test. At each visit, estimates for the adjusted changes from baseline in both the treatment and the placebo arm (adjusted for individual differences and differences in baseline and therapy status) as well as for the difference in changes between the two arms will be presented, including 95% confidence intervals (CI).

Subgroup analyses may be performed on the following variables:

- Country or center
- Psychotherapy at baseline
- Sex

Further details will be outlined in the SAP.

Descriptive summary statistics will be presented for both, absolute values and changes from baseline by visit and treatment arm.

Efficacy endpoints results will be plotted versus time individually and using means (absolute values and change from baseline) calculated by actual treatment arm.

9.3.6.Secondary Safety Analyses

Safety endpoints will be analyzed throughout the study from baseline to week 14, including:

- Number and frequency of Treatment Emergent Adverse Events (TEAEs) by severity
- Number and frequency of Serious TEAEs by severity
- Number and percentage of withdrawn participants due to TEAEs
- Frequency of physical examination parameters, vital signs, and ECG parameters of potential clinical concern
- Frequency of clinical laboratory parameters of potential clinical concern throughout the study
- Columbia – Suicide Severity Rating Scale (C-SSRS) results
- Number and frequency of concomitant medication intake throughout the study

The change from baseline to specific week will be analyzed for the following safety endpoints:

- Change from baseline to specific week in physical examinations, vital signs, and ECG parameters
- Change from baseline to specific week in clinical laboratory parameters

More details to specific endpoints are provided below.

Adverse Events

The total number of participants with at least one AE and the total number of AEs will be presented overall and by treatment arm and tabulated by MedDRA SOC and PT. In addition, AEs will be tabulated by worst severity and worst relationship to treatment.

The same tabulations will be provided for TEAEs, TEAEs of special interest, TEAEs leading to study drug discontinuation, serious TEAEs (STEAES) and STEAEs related to study medication.

Listings of participants with STEAEs, deaths and STEAEs leading to discontinuation and individual narratives for these cases will be provided.

Physical Examinations

Physical examination results including assessment as “normal” or “abnormal” and clinical significance of abnormalities will be listed. New abnormalities do not present at baseline will be flagged.

Vital Signs

All abnormal vital signs including assessment of clinical significance will be listed by participant. Summary statistics for vital sign parameters will be provided (absolute and change from baseline) by actual treatment arm and visit.

Electrocardiograms

All abnormal ECG results will be listed by participant including assessment of clinical significance and description of any abnormality. ECG parameters (absolute values and changes from baseline) will be summarized by actual treatment arm and visit.

Columbia-Suicide Severity Rating Scale

The C-SSRS results will be listed and summarized descriptively by actual treatment arm and visit.

Laboratory Safety Assessments

All abnormal laboratories including assessment of clinical significance will be listed by participant. Laboratory parameters (absolute values and changes from baseline) will be summarized by actual treatment arm and visit.

Shift tables will be produced for post-baseline time points and overall results per each parameter. Results will be defined as clinically significant abnormal > clinically non-significant abnormal > normal.

